## 7.5.2.3. Time-To-Event Efficacy Endpoints

For the time to achieve CHE-related Itch NRS score improvement of at least 4 points and time to achieve CHE-related Skin Pain NRS score improvement of at least 2 points, a log-rank test stratified by randomization stratification factors will be used for between treatment group comparisons. The hazard ratio and its 95% CI will be estimated based on the stratified Cox regression model using Efron's method accounting for ties. Kaplan-Meier curves will be presented by treatment groups. The number of participants, number of events and number of

censoring will be summarized by treatment groups. The Kaplan-Meier estimate of median time will be presented with its 95% CI. The 95% CI will be calculated using the method by Brookmeyer and Crowley (1982).

# 7.6. Analysis of Exploratory Efficacy Parameters

## 7.6.1. Exploratory Efficacy Analysis

#### 8. PHARMACODYNAMICS

## 8.1. Pharmacodynamic Analyses

Pharmacodynamic parameters will be summarized descriptively.

#### 9. SAFETY AND TOLERABILITY

Appendix A provides a list of data displays. Sample data displays are included in a separate document.

#### 9.1. General Considerations

The analyses in this section will be provided for the safety population in the DBVC and open-label evaluable population in the OLE period. Cumulative TEAEs across the treatment periods (DBVC and OLE periods) will be summarized. Summary tables may be replaced with listings when appropriate. For instance, an AE frequency table may be replaced with a listing if it only contains a few unique PTs reported on relatively few participants.

#### 9.2. Adverse Events

#### 9.2.1. Adverse Event Definitions

A TEAE is any AE either reported for the first time or worsening of a pre-existing event after first application of study drug and within 30 days of the last application of study drug. For participants who crossover treatments, the first application date is period-specific, and the end date is 30 days after the last application date in this period, or the first application date in the next period, whichever comes first. Analysis of AEs (as discussed below) will be limited to TEAEs, but data listings will include all AEs regardless of their timing in relation to study drug application.

Adverse events will be tabulated by MedDRA PT and SOC. Severity of AEs will be graded using the NCI CTCAE v5.0 (Grade 1 to 5). The CTCAE reporting guidelines and grading details are available on the Cancer Therapy Evaluation Program website.

The subset of AEs considered by the investigator to be related to study drug will be considered treatment-related AEs. If the investigator does not specify the relationship of the AE to study drug, the AE will be considered treatment-related. The incidence of AEs and treatment-related AEs will be tabulated. Serious AEs will also be tabulated.

Any missing onset date, causality, or severity must be queried for resolution. Unresolved missing causality and severity will be handled according to the following rules:

- An unresolved missing causality will be considered treatment-related.
- An unresolved missing severity will be identified as an unknown severity.

For purposes of analysis, all AEs will be considered TEAEs unless the AE can unequivocally be defined as not treatment-emergent.

Application site reactions are AEs that occur at the site of drug application. A summary of ASRs will be provided.

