6.5.2. Criteria for Permanent Discontinuation of Study Drug

The occurrence of unacceptable toxicity not caused by the underlying disease may require that the study drug be permanently discontinued. Unacceptable toxicity is defined as follows:

- The occurrence of an AE that is related to the study drug that, in the judgment of the investigator or the sponsor's medical monitor, compromises the participant's ability to continue study-specific procedures or is considered to not be in the participant's best interest.
- Worsening of CHE that requires treatment with a prohibited concomitant medication.
- An AE that requires an interruption of study drug for more than 2 weeks.
- Confirmed Grade 4 laboratory abnormalities related to study drug (see Section 6.5.1).

See Section 7 for discontinuation procedures.

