9.1. Definition of Adverse Event

Adverse Event Definition

- An AE is any untoward medical occurrence associated with the use of a drug in humans, whether or not it is considered drug related.
- An AE can therefore be any unfavorable or unintended sign (including an abnormal laboratory finding), symptom, or disease (new or exacerbated) temporally associated with the use of study drug.

Additional Guidance for Events Meeting the Adverse Event Definition

- Any safety assessments (eg, vital signs measurements), including those that worsen from baseline, considered clinically significant in the medical and scientific judgment of the investigator (ie, not related to progression of underlying disease) are to be reported as an AE.
- Abnormal laboratory test results are to be reported as an AE if they are considered clinically meaningful, induce clinical signs or symptoms, require concomitant therapy, or require changes in study drug. Whenever possible, a diagnosis (eg, anemia, thrombocytopenia) should be recorded in the eCRF rather than the abnormal laboratory test result (eg, low hemoglobin, platelet count decreased).
- Exacerbation of a chronic or intermittent pre-existing condition/disease, including either an increase in the frequency and/or intensity of the condition, is to be reported as an AE.
- New conditions detected or diagnosed after the start of study drug administration are to be reported as an AE.
- Signs, symptoms, or the clinical sequelae of a suspected drug-drug interaction are to be reported as an AE.
- Signs and/or symptoms from dose administration errors of a study drug (eg, overdose) or a concomitant medication are to be reported as an AE.
- "Lack of efficacy," "disease progression," or "failure of expected pharmacological action" will not be reported as an AE or SAE. Such instances will be captured in the efficacy assessments.
- A condition that leads to a medical or surgical procedure (eg, endoscopy, appendectomy) will be reported as an AE if it occurs after obtaining informed consent. If the condition is present before entering the study, then it should be captured as medical history.
- Pre-existing diseases or conditions with expected fluctuations in signs or symptoms should be reported as an AE only if the investigator judges the fluctuation to have worsened more than expected during study participation.

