#### 3. STUDY DESIGN

[figure not shown]
This is a Phase 2, randomized, double-blind, vehicle-controlled, 16-week study followed by a 16-week open-label treatment extension period. Approximately 180 participants with moderate to severe CHE with no history of (within the past 5 years) or current AD will be randomized 1:1 to either ruxolitinib 1.5% cream or vehicle cream. Participants will apply either ruxolitinib 1.5% cream or vehicle cream (both BID) to CHE lesions on the hands and wrists (if applicable) for 16 weeks. All areas identified at baseline should continue to be treated through the end of the DBVC period (Week 16) unless the participant meets criteria for stopping study drug.

At Week 16, participants with no safety concerns will enter the 16-week OLE period, during which all participants will receive open-label ruxolitinib 1.5% cream. Affected areas will be treated as needed until they clear during the OLE period.

Participants, investigators, and the sponsor will be blinded to each participant's treatment assignment during the DBVC period. During the OLE period, participants and investigators will remain blinded to the treatment assignment during the DBVC period until after all participants have completed treatment or discontinued and completed the safety follow up period.

Figure 1 presents the study design schema.

Figure 1: Study Design Schema

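### Application site reactions are defined by location alone, that location is the CHE lesion, and the protocol does not settle whether a CHE flare is an AE, so the headline ASR count can mix flares with local reactions

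*SAP*

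**What the plan says.** **ASR definition.** SAP 9.2.1: "Application site reactions are AEs that occur at the site of drug application". It carries no causality condition, term list or exclusion of the disease under study. SAP 3 has the cream applied to the CHE lesions of the hands and wrists, so the application site and the diseased skin are the same place.

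**What counts as an AE.** Protocol 9.1 has three relevant bullets:
- "Exacerbation of a chronic or intermittent pre-existing condition/disease" counts as an AE, whether the disease becomes more frequent or more intense. No exception is made for CHE.
- A pre-existing condition with expected fluctuation is an AE only when the investigator judges it to have become worse than expected.
- Lack of efficacy and disease progression "will not be reported as an AE or SAE. Such instances will be captured in the efficacy assessments".

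**Other signals.** Protocol 9.2 uses hospitalization for signs or symptoms of the study disease as an example of something that is not an AE. Protocol 6.5.2 opens its list with "The occurrence of unacceptable toxicity not caused by the underlying disease may require that the study drug be permanently discontinued", and then includes in that list "Worsening of CHE that requires treatment with a prohibited concomitant medication". Protocol 7.1.1 names disease worsening and unacceptable toxicity as two separate reasons for stopping treatment.

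**Outputs.** SAP 9.2.2 plans a count of participants with any ASR in the overall AE summary, ASRs by preferred term, treatment-related TEAEs, and TEAEs leading to discontinuation by system organ class and preferred term. Under SAP 9.2.1 a doubtful AE counts as treatment-emergent.

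**The concern.** A flare on the hands can reasonably be recorded as an AE at one site and left to the efficacy assessments at another, with both sites following the protocol. At the first site the SAP definition makes it an ASR with no further judgement. It then counts in the any-ASR line and, if it is the recorded reason for stopping, among TEAEs leading to discontinuation. At the second site it appears in neither.

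AE type, frequency and severity form a stated secondary safety endpoint (Protocol Table 4), and ASRs are the SAP's dedicated summary of events at the treated skin. The design assumes that ruxolitinib controls CHE better than vehicle (26% versus 10% treatment success, Protocol Table 9). On that premise recorded worsening would be more frequent on vehicle, and the headline ASR comparison in the double-blind period would then favour ruxolitinib for a reason that is efficacy rather than local tolerability.

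**Working it through.** **1. The rules side by side.** Protocol 9.1, applied to a CHE flare:

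| Bullet | Flare within expectation | Flare worse than expected |
|---|---|---|
| Exacerbation of a chronic condition | record | record |
| Expected fluctuation | do not record | record |
| Lack of efficacy or progression | do not record | do not record |

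The bullets disagree in both columns. The fluctuation bullet narrows the conflict and adds investigator judgement, but does not remove it. Protocol 9.2 points to not recording. Protocol 6.5.2 calls CHE worsening toxicity under a lead-in that excludes toxicity from the underlying disease, and 7.1.1 keeps the two apart.

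**2. The plan's own figures.** No ASR or flare rate is stated. The only related figures are the powers in Protocol Table 9, with 180/2 = 90 per arm. By the pooled-variance chi-square approximation,

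power = Φ{[√n·|p1 − p2| − 1.96·√(2p̄(1 − p̄))] / √(p1(1 − p1) + p2(1 − p2))}.

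This gives 80.3%, 90.9%, 95.9% and 92.5% against the stated 80%, 90%, 95% and 92%. They reproduce, and nothing below changes them.

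**3. Illustration with assumed rates.** Let t be the true local-reaction rate, f the rate of CHE worsening and r the share of worsening recorded as an AE. Take r as equal in both arms, and local reactions and flares as independent. Then

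observed ASR rate = 1 − (1 − t)(1 − f·r),

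and with equal t, vehicle minus ruxolitinib = (1 − t)·r·(f_veh − f_rux).

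With t = 5% in both arms, f_rux = 3% and f_veh = 10%:
- r = 0: 5.0% versus 5.0%.
- r = 0.5: ruxolitinib 1 − 0.95 × 0.985 = 6.4%; vehicle 1 − 0.95 × 0.95 = 9.8%; difference 0.95 × 0.5 × 7 = 3.3 points.
- r = 1: ruxolitinib 1 − 0.95 × 0.97 = 7.9%; vehicle 1 − 0.95 × 0.90 = 14.5%; difference 0.95 × 7 = 6.7 points, or about 7 versus 13 of 90.

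Range at r = 1, with t from 3% to 8% and worsening (ruxolitinib/vehicle) of 2/5%, 3/10% or 5/15%: from 0.92 × 3 = 2.8 points to 0.97 × 10 = 9.7 points.

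**4. A true excess on ruxolitinib.** With t = 6% on ruxolitinib and 3% on vehicle, and r = 1:
- Worsening 3/10%: 1 − 0.94 × 0.97 = 8.8% versus 1 − 0.97 × 0.90 = 12.7%. The order reverses.
- Worsening 2/5%: 1 − 0.94 × 0.98 = 7.9% versus 1 − 0.97 × 0.95 = 7.9%. The excess disappears.

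**5. Limits on sign and size.** With worsening equal at 10/10%, t = 5% and r = 1, both arms read 14.5%: inflated, with no difference between them. If worsening is allowed anywhere in 5–20% on vehicle and 1–8% on ruxolitinib, independently, with half recorded, the added difference (vehicle minus ruxolitinib, ignoring overlap with true reactions) runs from 0.5 × (5 − 8) = −1.5 to 0.5 × (20 − 1) = +9.5 points. The sign follows from the premise that the drug works, not from any figure in the documents.

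**The case against.** The strongest reply is that Protocol 9.1 can be read coherently. On that reading the study disease belongs to the efficacy assessments, and the exacerbation and fluctuation bullets govern other conditions; the example in Protocol 9.2 supports it. Protocol 6.5.2 is a criterion for stopping treatment and not a recording rule. This defeats the stronger reading that the protocol flatly requires and forbids the same record. It does not remove the ambiguity, because no sentence limits the exacerbation bullet to conditions other than CHE.

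A reader might also infer that flares would be counted as drug reactions. The documents do not support that. The investigator judges causality for each AE (Protocol 9.3), and treatment-related TEAEs are tabulated separately; only unresolved missing causality defaults to related. An ASR here is an event by place.

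The planned outputs also expose much of the problem. ASRs and TEAEs leading to discontinuation are shown by preferred term, and ASRs are listed, so eczema terms would be visible by arm. What stays mixed is the any-ASR line, with no prespecified rule for separating it.

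A location-only definition has merit: it is inclusive and needs no judgement. Simply removing hand dermatitis terms would drop true irritant or allergic reactions to a cream used on the hands. That stands, and the fix keeps the full count.

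Finally, Protocol 9.3 refers sites to eCRF guidelines for AE recording, the SAP places sample displays in a separate document, and Section 6.5.1 is not in the public text. Recording of CHE worsening may be settled there; this cannot be checked.

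**Conclusion.** The point holds as a gap in definition. The ASR rule is location-only, the location is the lesion, and the protocol sections do not give sites one answer for a CHE flare. Recorded flares therefore enter the headline ASR count, and possibly the discontinuation summary, without being separated from local reactions.

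A reader might go further and conclude that the plan is shown to be biased toward ruxolitinib. It is not. Bias in that direction requires recorded worsening to be more frequent on vehicle. That is plausible if the drug works, but the documents give neither flare rates nor recording shares. The 2.8 to 9.7 point range rests wholly on assumed rates with vehicle worse, and with equal worsening the difference is nil.

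The matter concerns a descriptive safety summary. The primary test, key secondary tests, alpha and power are untouched. The change is worth making because it is specific and nearly free.

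**What to change.** 1. **Protocol.** Reconcile Sections 6.5.2, 7.1.1, 9.1 and 9.2 so that all sites classify CHE worsening in the same way for AE recording. This concerns recording only; no change to the stopping criteria is proposed.
2. **SAP 9.2.1 and 9.2.2.** Keep the all-inclusive ASR count. Beneath it add two rows by arm: ASRs with preferred terms denoting the disease under study, and all other ASRs. Fix the term list before unblinding, which for the sponsor follows the primary database lock (SAP 10).
3. **TEAEs leading to discontinuation.** Add the same split.

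The cost is a site clarification, a short term list and extra rows in tables already planned. One downside remains: a true contact reaction coded to a hand dermatitis term would fall in the disease row. It stays in the total and remains visible by arm.

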#### 9.2.2. Adverse Event Summaries

An overall summary of AEs by treatment period will include:

- Number (%) of participants reporting any TEAEs
- Number (%) of participants who had any ASRs
- Number (%) of participants reporting any serious TEAEs
- Number (%) of participants reporting any Grade 3 or higher TEAEs
- Number (%) of participants reporting any treatment-related TEAEs
- Number (%) of participants who temporarily interrupted study drug in any of the treated areas because of TEAEs
- Number (%) of participants who permanently discontinued study drug because of TEAEs
- Number (%) of participants who had a fatal TEAE

The following summaries will be produced by MedDRA term (if 2 or fewer participants appear in a table, a listing may be appropriate):

- Summary of TEAEs by SOC and PT
- Summary of TEAEs by PT in decreasing order of frequency
- Summary of ASRs by MedDRA PT in decreasing order of frequency
- Summary of Grade 3 or higher AEs by SOC and PT
- Summary of Grade 3 or higher AEs by PT in decreasing order of frequency
- Summary of serious TEAEs by SOC and PT
- Summary of serious TEAEs by PT in decreasing order of frequency
- Summary of treatment-related TEAEs by SOC and PT
- Summary of treatment-related TEAEs by PT in decreasing order of frequency
- Summary of Grade 3 or higher treatment-related TEAEs by SOC and PT
- Summary of treatment-related serious TEAEs by SOC and PT
- Summary of TEAEs with a fatal outcome by SOC and PT
- Summary of TEAEs leading to dose interruption by SOC and PT
- Summary of TEAEs leading to discontinuation of study drug by SOC and PT

Adverse events of interest will be summarized in the following categories:

- Cytopenias
  - Anemia
  - Thrombocytopenia
  - Neutropenia
- Herpes zoster
- Nonmelanoma skin neoplasms
- Liver function test elevations
- Malignancies
- Major Adverse Cardiovascular Events
- Venous and arterial thromboembolic events
- Thrombocytosis and elevated mean platelet volume

## 9.3. Clinical Laboratory Tests

#### 9.3.1. Laboratory Value Definitions

All laboratory assessments will be performed using a central laboratory except for urine pregnancy tests (as applicable). Laboratory values and change from baseline values will be summarized descriptively by visit, and non-numeric test values will be tabulated when necessary.

The baseline value will be determined using the last nonmissing value collected before the first study drug application, prioritizing scheduled assessments for baseline identification over unscheduled visits. The last record before administration in the highest priority will be considered the baseline record. For baseline laboratory candidates with the same date and time in the same priority category, additional rules may be provided after consultation with the medical monitor to delineate which value will be defined as baseline.

#### 9.3.2. Laboratory Value Summaries

Clinical laboratory tests, including hematology and serum chemistry, will be performed at the Protocol-specified visits. If specific safety issues arise, additional unscheduled laboratory tests/analyses may be performed at the discretion of the investigator.

All test results and associated normal ranges from central laboratories will be reported in SI units. All tests with numeric values will have a unique unit per test. Any laboratory test results and associated normal ranges from local laboratories will be converted to SI units.

When there are multiple laboratory nonmissing values for a participant's particular test within a visit window, the laboratory value with the smallest laboratory sequence number will be used in by-visit summaries.

For test results that will be summarized with available normal ranges, the number and percentage of participants with the laboratory values being low (but never high), normal, high (but never

low), and both low and high will be calculated for each test. This shift summary will be produced for each test for the safety population in the DBVC period, as well as the open-label evaluable population in the OLE period. Shift tables will be presented showing change in CTCAE grade from baseline to worst grade postbaseline as well. The denominator for the percentage calculation will use the number of participants in the baseline category.

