8.3.4. Laboratory Assessments

See Table 8 for the list of clinical laboratory tests to be performed and Table 3 for the timing and frequency. A central laboratory will perform all clinical laboratory assessments for safety (eg, blood chemistries or hematology assessments) and will store the samples for PD analysis. Additional testing may be required by the sponsor based on emerging safety data. All Protocol-required laboratory assessments must be conducted in accordance with the Laboratory Manual and Table 3. Information regarding collection, processing, and shipping of samples for laboratory assessment is provided in the Laboratory Manual.

Clinically significant abnormal laboratory findings are those that are not associated with the underlying disease, unless judged by the investigator to be more severe than expected for the participant's condition. All laboratory tests with values considered clinically significantly

abnormal during participation in the study or within 30 days after the last application of the study drug should be repeated until the values return to normal or baseline or are no longer considered clinically significantly abnormal by the investigator or medical monitor.

It is not necessary to reassess chemistry or hematology at baseline (Day 1) if screening assessments were performed within 14 days of Day 1.

See Section 9.1 for information regarding laboratory abnormalities that should be recorded as an AE in the eCRF.

Table 8: Required Laboratory Analytes

Chemistry	Hematology	Serology	Pregnancy Testing
Albumin Alkaline phosphatase ALT AST Blood urea nitrogen or urea Creatinine Creatine kinase Glucose Total bilirubin Direct bilirubin (if total bilirubin is elevated above ULN)	Complete blood count, including: Hemoglobin Hematocrit Platelet count Red blood cell count Reticulocyte count White blood cell count Count Differential count (absolute and %), including: Basophils Eosinophils Lymphocytes Monocytes Neutrophils	HIV	Human chorionic gonadotropin (WOCBP only) FSH (women of nonchildbearing potential only)

Note: Additional tests may be required, as agreed by investigator and sponsor, based on emerging safety data or to rule out a diagnosis.

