8.6. Unscheduled Visits

Unscheduled visits may occur at any time medically warranted. Any assessments performed at those visits should be recorded in the eCRF.

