#### 4.1.3. Baseline Value

Baseline is the last nonmissing measurement obtained before or on the day of first application of ruxolitinib cream or vehicle cream for DBVC period.

For randomized participants not treated with any study drug, baseline is defined as the last nonmissing assessment before or on the day of randomization for all parameters.

For participants who continue in the OLE period, baseline for OLE is defined as follows:

- For efficacy evaluation, baseline is the last nonmissing measurement obtained before or on the day of first application of study treatment in DBVC period.
- For safety evaluation, for participants who cross over from vehicle group to ruxolitinib cream, the baseline is the last nonmissing measurement obtained before or on the day of first application of ruxolitinib cream in the OLE period; for participants on ruxolitinib cream in both periods, baseline is the last nonmissing measurement obtained before or on the day of first application of study treatment in DBVC period.

When scheduled assessments and unscheduled assessments occur on the same day and time of the assessment or time of first application is not available, use the following convention to determine baseline:

- If both a scheduled and an unscheduled visit are available on the day of the first application and the time is missing, use the scheduled assessment as baseline.
- If all scheduled assessments are missing on the day of the first application and an unscheduled assessment is available, use the unscheduled assessment as baseline.

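### SAP 9.3.2 picks by-visit laboratory values by smallest sequence number, with no priority for the scheduled draw and with sequence number and window left undefined, so an earlier unscheduled draw can displace the scheduled one

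*SAP*

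**What the plan says.** SAP 9.3.2 has one rule for the case where the same test has more than one result in a window: "the laboratory value with the smallest laboratory sequence number will be used in by-visit summaries". Unscheduled draws are not excluded, and the same section expects them: if safety issues arise, "additional unscheduled laboratory tests/analyses may be performed at the discretion of the investigator".

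Protocol 8.3.4 goes further. Tests with clinically significant abnormal values "should be repeated until the values return to normal or baseline or are no longer considered clinically significantly abnormal". Protocol 8.6 sends unscheduled results to the database: "Any assessments performed at those visits should be recorded in the eCRF".

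For the laboratory baseline, SAP 9.3.1 takes the last value before first application, "prioritizing scheduled assessments for baseline identification over unscheduled visits". SAP 4.1.3 has a similar rule when a scheduled and an unscheduled assessment fall on the day of first application and the time is missing: "use the scheduled assessment as baseline". Both are worded for baseline only.

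The SAP gives no definition of the laboratory sequence number and no numeric analysis window. The only windows in the documents are the visit windows of the protocol's schedule of activities, ±3 days at Weeks 2 to 32.

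**The concern.** A sequence number is a record index. It does not show whether a draw was scheduled or how near it was to the visit day. If numbering follows collection order, choosing the smallest means choosing the earliest result in the window. An unscheduled draw that comes before the scheduled one would then stand in for the visit. If numbering does not follow collection order, the choice is arbitrary. That second case is possible: SAP 9.3.2 provides for local laboratory results, and Protocol Appendix B allows off-site sampling, so results may reach the database from more than one source. Two programmers could build different by-visit tables from the present text.

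The displaced values would not be a random sample. Repeats are required after abnormal results and continue until they resolve, so extra draws should gather in participants with abnormal values. A table or box plot could then show an abnormality at a visit where the scheduled draw had already normalised.

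The two ends of a change from baseline also rest on different principles: scheduled first and then last before treatment at baseline, smallest index regardless of schedule afterwards.

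**Working it through.** The plan states no figure that depends on this rule, so there is none to reproduce. The check is day counting plus a simple sensitivity calculation.

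**Inputs from the documents**
- Scheduled chemistry and hematology in the treatment period after baseline: Weeks 8, 16, 24 and 32 (protocol schedule of activities). None at Week 12.
- Study day = date − Day 1 date + 1 (SAP 4.1.2), so Week 8 = 8 × 7 + 1 = Day 57, Week 12 = Day 85, Week 16 = Day 113, Week 24 = Day 169.
- About 180 participants randomized 1:1, so 90 per arm.

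**Assumptions, not in the documents**
- Sequence numbers run in collection order across scheduled and unscheduled draws.
- Window type, varied below. For midpoint windows, the boundary day goes to the earlier visit.

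**Step 1: the ordinary retest.** A repeat 1 to 3 days after an abnormal scheduled draw on Day 57 falls on Days 58 to 60. It lies in the same ±3-day window (Days 54 to 60) but has a larger number, so the scheduled value is kept. A repeat 4 to 52 days later (57 + 4 = 61 to 57 + 52 = 109) lies in neither the Week 8 nor the Week 16 window of ±3 days.

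**Step 2: when displacement occurs.** The unscheduled draw must be in the window and before the scheduled one. For Week 16:

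| Window | Days covered | Draws that replace a Day 113 value | Most days early |
|---|---|---|---|
| ±3 days (protocol visit window) | 110–116 | 110–112 | 3; 6 if the scheduled draw is on Day 116 |
| Midpoints between all visits (assumed): (85 + 113)/2 = 99 | 100–141 | 100–112 | 13 |
| Midpoints between laboratory visits (assumed): (57 + 113)/2 = 85 | 86–141 | 86–112 | 27 |

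The upper limit in the last two rows is (113 + 169)/2 = 141. Counted from a Week 8 draw on Day 57, the ±3-day case needs an extra draw 53 to 55 days later (110 − 57 to 112 − 57). The widest case needs one 29 to 55 days later. The last two rows are illustrative only.

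**Step 3: size.** If k of 90 participants are displaced by D standard deviations each, the arm mean at that visit moves by k × D / 90. Both k and D are assumed.
- k = 1, D = 0.5: 1 × 0.5 / 90 = 0.006 SD
- k = 2, D = 1: 2 × 1 / 90 = 0.022 SD
- k = 5, D = 2: 5 × 2 / 90 = 0.11 SD

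**Step 4: which outputs use the selected value.** By its wording, the rule applies to by-visit summaries: descriptive values and changes from baseline (SAP 9.3.1), and the by-visit box plots of hemoglobin, platelets, neutrophils and other hematology tests (SAP Appendix A). The CTCAE shift tables use each participant's worst grade after baseline. The low/normal/high summary asks whether a participant was ever low or ever high. Neither uses the by-visit selection.

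**The case against.** The rule is prespecified and blind to the result. In the common case, a retest prompted by an abnormal scheduled draw, it keeps the scheduled value. With the only window in the documents, displacement needs an unscheduled draw within a few days before the visit. Anything larger depends on a window that the SAP does not state, and the longest lead time also requires windows that skip Week 12. Safety conclusions do not rest on these summaries: worst-grade shifts, the low/high classes, listings of abnormal values and the cytopenia category among adverse events of interest are all planned, and Protocol 10.4.4 plans no formal between-arm comparison of laboratory data. The scheduled-first rule in SAP 9.3.1 is confined to baseline, so nothing is contradicted.

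All of this stands, and it limits the size of the point. It does not supply the missing definitions of sequence number and window. Nor does it give a reason for selecting a visit value by an index unrelated to the visit, when the SAP already uses scheduled-first selection at the other end of the change from baseline.

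**Conclusion.** The by-visit selection rule is under-specified and takes no account of scheduled status or closeness to the visit day. If numbering is chronological, an earlier unscheduled draw in the same window can displace the scheduled one, mainly in participants with abnormal values. This is rare with ±3 days and more likely under wider contiguous windows, which would be an assumption. Under the assumed range above, an arm mean would move by about 0.006 to 0.11 SD; the documents give no basis for a firmer figure. The effect stops at descriptive by-visit values, changes from baseline and box plots.

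A reader might infer more, in three ways that the documents do not support:
- That retests will routinely replace scheduled draws. Displacement requires both chronological numbering and an extra draw before the scheduled one, and the SAP establishes neither.
- That SAP 9.3.2 contradicts SAP 9.3.1. The approaches are inconsistent, but the earlier section speaks only of baseline.
- That safety signals or efficacy results are at risk. The worst-grade shift tables, the low/high classes and all efficacy analyses are outside this rule.

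This is an inexpensive improvement, not a flaw that threatens a conclusion.

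**What to change.** In SAP 9.3.2, replace the selection sentence with an ordered rule for postbaseline by-visit summaries:
1. use the scheduled assessment;
2. if there is none, use the assessment closest to the target day;
3. if two are equally close, use the later;
4. use the sequence number only as the last tie-break.

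State the numeric analysis window for each laboratory visit, and say how sequence numbers are assigned across scheduled, unscheduled and local results. Other orderings could be defended; what matters is that the rule refers to the visit and can be reproduced. The worst-grade and low/high tables need no change.

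The cost is a few sentences in the SAP and a standard programming step, with no effect on data collection, sample size or the testing sequence.
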